1.3 Research Design and Methods

RR-MS patients will be recruited from the Robert Wood Johnson Center for MS under the direction of [name]. The patients will be asked to participate in the study during their regular clinical visit to the MS Center.

Inclusion criteria includes patients aged 21-65 Relapsing Remitting Multiple Sclerosis (RRMS) who met the 2017 McDonald criteria.

The first group (**Group A**) of MS patients (**n=25**) will receive a dietary fiber supplementation. They will consume 60 g/day of HFS for 12 weeks (High-fiber supplement group, Group-A). The supplement consists of a mixture of soluble fibers (from inulin and fibersol-2) and insoluble fibers (from oat bran, corn bran, wheat bran and sorghum bran) and it will be consumed as a drink.

The second group of MS patients (**Group B**) (**n=25**) will not consume any high fiber supplement.

The first group (**Group C**) of healthy volunteers (**n=25**) will receive a dietary fiber supplementation. They will consume 60 g/day of HFS for 12 weeks. Healthy volunteers will not have MS.

The second group (**Group D**) of healthy volunteers (**n=25**) will not consume any high fiber supplement.

For Groups A, B, C & D stool, and serum samples will be collected at 3 time points (baseline; Week 8; & Week 12).

Group E (n=25) will consist of 25 subjects with MS who experience an MS flare up.

These 25 subjects can be those participants with MS who are already part of the above study (Group A or B) and consent to 2 extra blood and 2 extra fecal samples collected at the time of the acute flare up and upon resolution of symptoms.

Screening visits will typically take place during routine MS follow up visit at the Robert Wood Johnson Center for MS. During this time, eligibility will be reviewed, and consent will be obtained once the patient has had time to review the study, have questions answered, and agree to participate. During this screening visit, details regarding the patients MS history, food allergies/intolerances, medical history, and medications will be recorded. Eligible participants will be asked to provide blood and stool samples for baseline assessment.

A. Research Procedures

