Sept. 2021-Aug. 2023 Fecal transplantation in germ free mice and analysis for EAE

D. Endpoints

The primary endpoint will be detection of effect of HFS on intestinal microbial composition, intestinal permeability, production of SCFA, intestinal permeability, and immune cells in 25 MS patients between before and after intake of high-fiber supplement.

The secondary endpoint will be detection of biomarkers for intestinal inflammation-associated disease exacerbation in 25 MS patients.

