1.6 Study Variables

A. Independent Variables, Interventions, or Predictor Variables

Experiment 1: Four groups (HDs and MS patients with and without HFS treatment).

Experiment 2: Four groups (Fecal samples from HDs and MS patients with & without HFS treatment).

Experiment 3: Two groups (MS patients with MS relapse and healthy volunteers).

B. Dependent Variables or Outcome Measures

Experiment-1: Percentage of pathogenic and non-pathogenic bacteria, intestinal permeability, and percentage of pathogenic and regulatory immune cells.

Experiment-2: Incidence and severity of EAE development.

Experiment-3: Intestinal inflammation and intestinal permeability.

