4.0 Subject Considerations

4.1 Subject Selection and Enrollment Considerations

A. Method to Identify Potential Subjects

2017 McDonald criteria will be used to select relapsing remitting MS patients. Age and sex matched healthy donors will be recruited from Rutgers students/staff volunteers or New Jersey local resident using e-mail with study flyers.

B. Recruitment Details

The study will recruit both participants who have MS and Healthy Volunteers. Subjects will be recruited at RWJ Center for Multiple Sclerosis ambulatory clinic.

Patients will be recruited from the outpatient neurology clinic of the Rutgers Robert Wood Johnson Center for MS. The patients will be asked to participate in the study during their regular clinical visit to RWJ MS Center. Only if the patient agrees to participate and meets enrollment criteria will they be enrolled in the study.

Healthy volunteers will be recruited from Rutgers students/staff volunteers or New Jersey local resident. There will be no undue influence on students / staff. Participation is completely voluntary. The healthy donor recruitment flyer will be emailed to students / staff. Those who are interested can reach out to obtain further information and be screened for eligibility.

C. Subject Screening

Subjects will be screened by [name] at RWJ MS center based on inclusion and exclusion criteria laid out in this study.

▪ Inclusion Criteria

1. Patients who meet 2017 McDonald criteria for RRMS.
2. Both males and females (age 21-65 year old).
3. Newly diagnosed and RRMS patients who are taking non-oral MS medications like interferon, Copaxone and Tysabri.
4. RRMS patients who refuse to take MS medications but are interested in other interventions.
5. Healthy volunteers without any chronic inflammatory or autoimmune diseases will be included in the study as controls.

Exclusion Criteria

1. Primary or secondary progressive MS.
2. Patients with autoimmune comorbidities.
3. Having received prior chemotherapy.
6. Pregnant women.
7. Cognitively impaired.
8. Antibiotic use within last 6 months.
9. Probiotic use within the last 2 months.

10. Self-reported allergy or intolerance to any ingredients in the fiber supplement.
110. Self-reported or diagnosed gastrointestinal disorders (such as; Irritable Bowel Syndrome, Diverticulitis, Chron's Disease)
121. Active or history of malignant tumors

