5.0 Special Considerations

5.1. Life style consideration

Since the risks of study drug on embryofetal development are unknown, participants in Group A and Group C will be required to use contraception methods.

Men and women of childbearing potential participating in this study will be required to use contraception from study recruitment until 30 days after the last day of study participation. Acceptable forms of contraception:

For men with female partners of childbearing potential:

1. Agree to use male condom.
2. Abstinence is an acceptable method only if it is consistent with the preferred and usual lifestyle of the patient

For women of childbearing potential:

1. Agree to use highly effective contraception method below:
 - 1-1. Combined (estrogen and progesterone-containing) hormonal contraception by oral, intravaginal, or transdermal method.
 - 1-2. Progesterone-only hormonal contraception by oral or injectable method.
 - 1-3. Intrauterine device.
 - 1-4. Bilateral tubal occlusion.

1-5. Vasectomized partner.

2. Abstinence is an acceptable method only if it is consistent with the preferred and usual lifestyle of the patient.

Men should refrain from donating sperm and women from donating eggs during the specified duration as well.

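### The plan gives no method for assigning participants to HFS or no HFS and no adjustment for baseline differences, so the A-versus-B and C-versus-D comparisons are open to confounding

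*Combined protocol and SAP*

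**What the plan says.** Section 1.3 sets up four groups of 25: MS patients with HFS (A) and without (B), and healthy donors with HFS (C) and without (D). Groups B and D "will not consume any high fiber supplement"; no placebo or blinding is described. Section 1.6 makes these four groups the independent variable for Experiment 1, and Experiment 2 uses stool from the same four groups in mice. Section 1.5 sizes the study per group.

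The primary endpoint (section 1.3 D) is worded differently, as an effect "in 25 MS patients between before and after intake of high-fiber supplement".

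The eligibility list in section 4.1 is common to all groups. For MS patients it admits "Newly diagnosed and RRMS patients who are taking non-oral MS medications like interferon, Copaxone and Tysabri" and also "RRMS patients who refuse to take MS medications but are interested in other interventions". Healthy donors are to be age- and sex-matched, but no matching of A to B or of C to D is stated.

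One rule names particular arms. Sections 1.3 A and 5.1 both say that "participants in Group A and Group C will be required to use contraception methods". The following paragraph of section 5.1 applies contraception to men and women of childbearing potential in the study, without naming groups.

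Section 6.1 Data Analysis has a heading and no text.

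**The concern.** Untreated controls isolate the effect of HFS only if they resemble the treated participants in everything else that moves the outcomes. When the assignment method is unstated and the intervention is visible, patient or staff preference can decide who takes HFS. Two features of the plan give preference something to act on.

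- **MS-drug status.** It ranges from none to several immune-active treatments, and the outcomes are regulatory and pathogenic T cells, PD-1/PD-L1 expression, cytokines, microbiota and permeability. Drug status is an obvious candidate confounder.
- **Contraception.** If it is required only in A and C, willingness to take part in those arms may depend on age, sex and family plans.

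Any imbalance would carry over to the mouse experiments, because the donor stool comes from the same groups.

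**Working it through.** **Step 1. Look for an assignment rule.** These are the sections where one would be expected:

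| Section | Content on groups | Assignment method |
|---|---|---|
| 1.3 Design and Methods | Defines A to D by HFS intake | None |
| 1.3 A Procedures | HFS supply, follow-up, contraception in A and C | None |
| 1.5 Sample size | 25 per group | None |
| 1.6 Study variables | Four-group comparison | None |
| 4.1 Selection | One eligibility list for all arms | None |
| 4.3 Number of subjects | 50 MS patients, 50 healthy donors | None |
| 6.1 Data Analysis | Empty | No adjustment |

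No randomisation, sequence, concealment, alternation or stratification appears. The only use of the word random is in the name of the Random Forest method.

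**Step 2. The plan's own figure.** Section 1.5 gives n = 20 per group at 5% type I error and 80% power. The mean difference and SD are not given, so the figure cannot be reproduced. Taking the test as two-sided (an assumption), it can be inverted: d = √(2/n) × (1.960 + 0.842).

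- n = 20: d = 0.316 × 2.802 = 0.89 (t-test 0.91).
- n = 25: d = 0.283 × 2.802 = 0.79 (t-test 0.81).

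These are the effects, in SD units, against which a spurious shift can be judged.

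**Step 3. How large could a spurious shift be?** The documents give no imbalance, so every input here except n = 25 per arm is an assumption: no true HFS effect, a two-sided 5% unadjusted comparison at Week 12, and one binary factor (takes no MS drug) with share pA in Group A and pB in Group B that shifts the outcome by g within-stratum SDs.

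- Bias: b = g(pA − pB).
- SD: s = √{[2 + g²pA(1 − pA) + g²pB(1 − pB)]/2}.
- Standard error: SE = s√(2/25); ratio r = b/SE.
- False-positive rate: 1 − Φ(1.96 − r) + Φ(−1.96 − r).

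Example with 50% versus 10% and g = 1: b = 0.40; s = √[(1.25 + 1.09)/2] = 1.082; SE = 1.082 × 0.283 = 0.306; r = 1.31; rate = 25.8%.

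| Drug-free share, A vs B | g = 0.5 | g = 1.0 |
|---|---|---|
| 30% vs 30% | 5.0% | 5.0% |
| 25% vs 15% | 5.3% | 6.2% |
| 40% vs 20% | 6.4% | 9.9% |
| 40% vs 10% | 8.1% | 16.6% |
| 50% vs 10% | 10.6% | 25.8% |
| 60% vs 10% | 13.9% | 37.4% |

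The bias b does not depend on n, so enrolling more people does not reduce it.

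**Step 4. Does change from baseline cure it?** If the factor adds the same g at baseline and at Week 12, the bias in the change is g(pA − pB) − g(pA − pB) = 0, and the rate returns to 5%. If the factor alters the 12-week change itself by h, a bias of h(pA − pB) remains. A newly diagnosed patient who starts a drug during the 12 weeks would be an example.

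**Step 5. Why stratify as well?** With simple randomisation and an assumed drug-free share of 30%, the chance difference in share between arms has SD √(2 × 0.3 × 0.7/25) = 0.13. Stratifying largely removes this.

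**The case against.** The strongest reply has four parts.

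1. **The documents are silent.** A reader might infer that participants are known to be assigned non-randomly. The text does not say that, nor that participants choose, and a few pages were not available to check. This stands: the finding is that no method is stated in the sections where it belongs.
2. **No criterion steers anyone.** A reader might infer that patients who refuse MS drugs are directed to HFS. The criterion applies to all MS participants and is tied to no arm. Under random assignment it would create no systematic imbalance. Clustering in Group A is a possibility that depends on choice of arm.
3. **The contraception rule is unclear.** Groups A and C are named twice, but the general sentence in section 5.1 can be read as covering everyone. A reader might infer that people who decline contraception can join only B or D; the documents do not say so. Nor do they link contraception to MS-drug status.
4. **The primary endpoint is a within-person contrast.** With baseline samples in all groups, stable differences cancel in change from baseline. This is correct and limits the problem. It does not remove it: a before-versus-after change in Group A alone cannot separate HFS from time effects or regression to the mean. Groups B and D can make that separation only if they are comparable.

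**Conclusion.** The point holds as a gap in design and analysis. No assignment method and no adjustment are stated, the control is open, and MS-drug status is mixed, so the A-versus-B and C-versus-D comparisons are open to self-selection and confounding by disease-modifying treatment, age or sex. The documents do not support saying that the comparisons are confounded, or that the control groups are useless; controls still give information on time trends.

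The size and direction cannot be derived from the plan. Over the assumed range the false-positive rate of an unadjusted Week 12 comparison runs from barely above 5% to about 37%, and no single value in the table deserves to be quoted as the expected one. An analysis of change from baseline would be affected only through differences in trajectory. The plan specifies neither analysis. Because randomisation closes the gap at little cost, the change should be made.

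**What to change.** - Randomise MS patients 1:1 to A or B, stratified by current disease-modifying treatment (none versus any), and healthy donors 1:1 to C or D. Allocate after consent, baseline samples and agreement to the participation requirements, from a list concealed from recruiting staff.
- Fill section 6.1 with a between-arm comparison at Week 12 within MS patients and within healthy donors, adjusted for the baseline value and, in MS patients, the stratum. Align the primary endpoint wording with it.
- Reconcile the contraception sentences in sections 1.3 A and 5.1 so that it is clear to which groups they apply.
- If the sponsor does not randomise, state this and how groups are formed, name the adjustment covariates in advance (at least MS-drug status, age, sex and the baseline value), and limit between-arm conclusions to association.

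Cost: a randomisation list, a protocol amendment and a short analysis section. The planned 25 per group need not change. The downside is that participants cannot choose their group, and some may decline for that reason.

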These 25 subjects will be those participants with MS who are already part of the above study (Group A or B) and consent to 2 extra blood and 2 extra fecal samples collected at the time of the acute flare up and upon resolution of symptoms. These subjects will be asked to sign a separate consent form agreeing to be part of the MS flare up group (n=25). Since around 50% of RRMS patients relapse at least once per year, we anticipate recruiting 25 relapsing RRMS patients from Group A and B in 1 years (2). RRMS flare up and resolution will be determined by [name].

Table-1. Schedule of specimen collection

Screening/Baseline assessment	8 weeks post HFS	12 weeks post HFS	Unscheduled visit at MS Relapse	Unscheduled visit at MS remission
MS history Medical history Medication history Food Allergy Consent Blood draw* Fecal collection*	Blood draw Fecal collection	Blood draw Fecal collection	Blood draw** Fecal collection**	Blood draw Fecal collection

--	--	--	--

*Sample collection will be done on the day of screening or before high fiber supplement.

** Sample collection will be done at MS relapse before steroid treatment.

Sample collection:

1. Stool Sample: Subjects will be asked to collect a single-stool sample without any laxative or dietary restrictions using a sample collection kit (Appendix 1). The collected stool sample will be brought to the MS research laboratory by the participants. If participants cannot bring the stool sample to the MS research laboratory, our lab staff will pick up the stool sample. The stool sample will be examined for the composition of gut bacteria. The stool sample will also be transplanted into an animal model of MS and examined for the development of experimental autoimmune encephalomyelitis (EAE).

2. Blood Draw: All participants will visit RWJ MS center to provide a blood specimen. Each subject will have a blood draw (80ml – about 5 tablespoons) as shown in Table-1. The immune cells will be isolated from each blood specimen and the presence of pathogenic and regulatory immune cells will be analyzed.

*NOTE: It is requested that all blood work be fasting. Nothing to eat or drink 10-12 hours before blood draw. Subjects may have water &/or black coffee /tea.

Fasting is very important to check the levels of short-chain fatty acid in the serum.

B. Experiment

1. Examine the effect of HFS on production of SCFA, intestinal microbial composition, and intestinal permeability

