1.4 Preliminary Data

A. A high-fiber supplement selectively promotes a group of SCFA producing bacteria.

Recently, our collaborator, [name] at our institution, developed a high-fiber supplement (HFS). His study suggests an association between intake of HFS and reduced gut dysbiosis and

increased abundance of short chain fatty acid (SCFA)-producing gut bacteria, and demonstrated that HFS can ameliorate type-2 diabetes mellitus (T2DM) (1). This beneficial effect was associated with increased levels of SCFA, butyric acid (Fig.1B). Furthermore, HFS promoted the growth of 15 SCFAs-producing bacteria which mostly peaked at day 28 and remained stable afterward till the end of the trial (Day 84), while only 3 acetate producers among the 15 SCFA-producing bacteria were promoted in controls (Fig.1C). To test whether HFS-promoted microbiota can contribute to glucose homeostasis, fecal samples isolated from HFS-treated (W group) and non-treated (U group) T2DM patients were transplanted into germ-free mice and glucose homeostasis was examined in the transplanted mice. As shown in Fig.2, the transplanted microbiota from HFS-treated group improved glucose homeostasis. Since increase in SCFAs-producing bacteria may be beneficial for inflammatory diseases including MS, we will investigate whether HFS can promote the growth of SCFAs-producing bacteria in MS patients and promote the development of regulatory immune cells.

[figure not shown]

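### Current users of fibre or prebiotic supplements are neither excluded nor recorded, so a pre-HFS baseline may already be partly fibre-exposed and the before/after change biased toward no effect

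*Combined protocol and SAP*

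**What the plan says.** Two exclusions in Section 4.1 C keep recent outside influences off the baseline microbiota: "Antibiotic use within last 6 months" and "Probiotic use within the last 2 months". The only exclusion that mentions fibre is "Self-reported allergy or intolerance to any ingredients in the fiber supplement", which concerns tolerance and not prior use.

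At screening (Section 1.3), "details regarding the patients MS history, food allergies/intolerances, medical history, and medications will be recorded". Table-1 lists the same kinds of history. Neither names usual diet or supplement use.

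On the baseline sample, the Table-1 footnote says: "Sample collection will be done on the day of screening or before high fiber supplement". No washout is given, and stool is collected "without any laxative or dietary restrictions". Section 1.3 B treats this sample as the time point before HFS.

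Groups B and D "will not consume any high fiber supplement" (Section 1.3). Nothing is said about a participant who already takes such a product at enrolment.

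The primary endpoint (Section 1.3 D) compares 25 MS patients before and after the supplement. Section 1.4 A reports that, in the earlier diabetes study, the fibre-promoted bacteria rose to levels "which mostly peaked at day 28 and remained stable afterward till the end of the trial (Day 84").

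**The concern.** The plan screens out two neighbouring exposures but not the one it is testing. HFS is a bran product, and Section 1.3 also describes inulin and a second soluble fibre as components. Someone already taking a bran or inulin product could meet every visible criterion. One inclusion item also admits patients who decline MS drugs and want other approaches. Supplement use is plausible in that group, though the documents do not show it.

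If such a person enters Group A or C, the baseline is partly exposed and the change to weeks 8 and 12 understates the response. Since the primary endpoint is a before/after change, similar prior use in the control group does not repair it.

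The between-group comparison is exposed as well. Allocation is not described as random, so equal prior use cannot be assumed. With no dedicated record of fibre use, the analysts would have no reliable way to identify these participants or adjust for them.

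**Working it through.** **Inputs from the documents:** 25 per group enrolled, 20 per group calculated, 5% type I error and 80% power (Section 1.5).

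**Inputs assumed, because the documents do not give them:** the share of prior users u (0-30% shown); the part k of the full response R that a prior user still shows on HFS (k = 0 is the worst case); two-sided testing; an unchanged standard deviation.

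**The plan's own figure.** The 20 per group cannot be reproduced, because no mean difference, standard deviation or sidedness is stated. Back-solving by the normal approximation gives a standardised difference of (1.960 + 0.842) × √(2/20) = 0.886 between two groups. For a one-sample change the equivalent is 2.802/√20 = 0.626. The gap claimed here does not dispute the 20. It serves only as a reference effect.

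**Before/after change in Group A.** Mean change = R × [1 − u(1 − k)]. With k = 0 this is R(1 − u). At n = 25 the standardised signal is 0.626 × √25 = 3.132 before dilution, so power = Φ(3.132 × (1 − u) − 1.960).

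| u (assumed) | Users among 25 | Mean change left | Power |
|---|---|---|---|
| 0 | 0 | 100% | 0.88 |
| 10% | 2.5 | 90% | 0.81 |
| 20% | 5 | 80% | 0.71 |
| 30% | 7.5 | 70% | 0.59 |

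If users still show half the response (k = 0.5), 20% users leave 1 − 0.20 × 0.5 = 90% of R, and power is 0.81.

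**HFS-minus-control contrast in change from baseline, k = 0.** Two readings of the control rule are possible.

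- *Controls stop a personal product and lose the full response.* Contrast = R(1 − u_HFS + u_control). With 20% users in the HFS group only, it is 0.8R. With 20% in the control group only, it is 1.2R. With 20% in both, 1 − 0.20 + 0.20 = 1.0R, so the two errors cancel.
- *Controls continue a personal product.* They show no change, so the contrast is R(1 − u_HFS). With 20% users in both groups it is 0.8R, and nothing cancels. If week-12 levels are compared instead of changes, all HFS participants are exposed and so is a share u_control of controls. The contrast is then R(1 − u_control), again 0.8R at 20%.

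The same omission can therefore shrink the contrast, inflate it or leave it unchanged. The result depends on where users fall and on how the control rule is read.

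**The case against.** Three stronger readings are tempting, and the documents do not support them.

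- *That controls must stop and will show a withdrawal effect.* A reader might infer this from the rule for Groups B and D. No stop instruction appears, however, and high-fiber supplement is the protocol's own name for the study product. The sentence may mean only that these groups do not receive it. An inflated contrast is one possibility among several.
- *That recent use fully determines the baseline because the bacteria peak by day 28.* That time course comes from a whole-diet intervention in type 2 diabetes, with whole grains, medicinal foods and prebiotics. It shows onset. It does not show the effect of a personal bran or inulin product, or how fast an effect fades. A prior user who adds HFS may well respond further.
- *That nothing recorded could reveal prior use.* Medication history may catch some products, and baseline bacterial composition and SCFA are measured. Neither identifies fibre use reliably.

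It is also fair to say that the 10-20% share is assumed, that the gastrointestinal exclusion removes some likely fibre users, and that at 10% users even the worst case leaves power near 0.81. The exclusion numbering jumps from 3 to 6, and the supplement and phone-call appendices are not in the available text, so the gap is established only for what can be read. Excluding supplement users also does not make a baseline free of fibre, since ordinary diet remains.

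What survives is that nothing visible excludes, washes out or systematically records prior use of the exposure under test.

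**Conclusion.** The concern holds in limited form. As written, a current fibre or prebiotic user can be enrolled in any group. In Groups A and C that biases the before/after change toward no effect. The loss is at most u × R, or 10-20% of the effect if 10-20% are users, and less if they still respond. Under the reference effect, that worst case takes power at n = 25 from 0.88 to 0.81 or 0.71. This uses most or all of the margin gained by enrolling 25 instead of 20.

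The effect on the between-group contrast is of the same order (0.8R to 1.2R with 20% users in one group only), but its direction cannot be settled from the plan. All of these sizes rest on an assumed user share. The omission itself does not. It is worth correcting because it touches the primary endpoint and is cheap to close. It does not invalidate the design.

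**What to change.** 1. Add an exclusion to Section 4.1 C for all four groups: no fibre or prebiotic supplement within a defined period before baseline. The 2 months already used for probiotics is a convenient example, though the documents offer no evidence that it is the right interval for fibre. Reconfirm at the baseline sample.
2. Add to screening and Table-1 a question on fibre and prebiotic supplements and a short item on usual fibre intake, so that baseline intake is available as a covariate. Name that covariate in Section 6.1, which has a heading but no text in the available copy.
3. State in Section 1.3 what Groups B and D may take during the study, and ask about it at weeks 8 and 12.
4. When defining the excluded products, reconcile the two descriptions of HFS. Section 1.3 includes inulin and a second soluble fibre, while the percentage formula in Section 1.7 lists only brans and xanthan gum.

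The cost is one criterion and one or two questions, with no change to the sample size. A few current users would be excluded or delayed. Ordinary dietary fibre will still vary, which is why the intake item is needed alongside the exclusion.
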